2.2.3 Non-Amgen Investigational Product Background: Pembrolizumab

Pembrolizumab is a potent humanized IgG4 monoclonal antibody with high specificity of binding to the PD-1, thus inhibiting its interaction with PD-L1 and PD-L2. Based on preclinical in vitro data, pembrolizumab has high affinity and potent receptor blocking activity for PD-1. Pembrolizumab has an acceptable preclinical safety profile and is in

clinical development as an IV immunotherapy for advanced malignancies. Keytruda® (pembrolizumab) is indicated for the treatment of patients across a number of indications. For more details on specific indications refer to the [Investigator's Brochure](#).

Refer to the [Investigator's Brochure/approved labeling](#) for detailed background information on pembrolizumab.

Therapeutic studies of pembrolizumab in mouse models have shown that administration of antibodies blocking PD-1/PD-L1 interaction enhances infiltration of tumor-specific CD8+ T cells and ultimately leads to tumor rejection, either as a monotherapy or in combination with other treatment modalities ([Spranger et al, 2014](#); [Curran et al, 2010](#); [Pilon-Thomas et al, 2010](#); [Weber, 2010](#); [Hirano et al, 2005](#); [Blank et al, 2004](#); [Strome et al, 2003](#)). Anti-mouse PD-1 or anti-mouse PD-L1 antibodies have demonstrated antitumor responses in models of squamous cell carcinoma, pancreatic carcinoma, melanoma, AML and colorectal carcinoma ([Curran et al, 2010](#); [Pilon-Thomas et al, 2010](#); [Nomi et al, 2007](#); [Zhang et al, 2004](#); [Strome et al, 2003](#)). In such studies, tumor infiltration by CD8+ T-cells and increased IFN-gamma, granzyme B and perforin expression were observed, indicating that the mechanism underlying the antitumor activity of PD-1 checkpoint inhibition involved local infiltration and activation of effector T cell function *in vivo* ([Curran et al, 2010](#)). Experiments have confirmed the *in vivo* efficacy of anti-mouse PD-1 antibody as a monotherapy, as well as in combination with chemotherapy, in syngeneic mouse tumor models (see the pembrolizumab Investigator's Brochure).

The importance of intact immune surveillance function in controlling outgrowth of neoplastic transformations has been known for decades ([Disis et al, 2010](#)).

Accumulating evidence shows a correlation between tumor-infiltrating lymphocytes in cancer tissue and favorable prognosis in various malignancies. In particular, the presence of CD8+ T cells and the ratio of CD8+ effector T cells/FoxP3+ regulatory T cells (T-reg) correlates with improved prognosis and long-term survival in solid malignancies, such as ovarian, colorectal, and pancreatic cancer; hepatocellular carcinoma; malignant melanoma; and renal cell carcinoma. Tumor-infiltrating lymphocytes can be expanded *ex vivo* and reinfused, inducing durable objective tumor responses in cancers such as melanoma ([Hunder et al, 2008](#); [Dudley et al, 2005](#)).

The PD-1 receptor-ligand interaction is a major pathway hijacked by tumors to suppress immune control. The normal function of PD-1, expressed on the cell surface of activated T cells under healthy conditions, is to down-modulate unwanted or excessive immune

responses, including autoimmune reactions. PD-1 (encoded by the gene *Pdcd1*) is an Ig superfamily member related to CD28 and cytotoxic CTLA-4 that has been shown to negatively regulate antigen receptor signaling upon engagement of its ligands (PD-L1 and/or PD-L2) (Greenwald et al, 2005; Okazaki et al, 2001). The structure of murine PD-1 has been resolved (Zhang et al, 2004).

PD-1 and its family members are type I transmembrane glycoproteins containing an Ig variable-type (IgV-type) domain responsible for ligand binding and a cytoplasmic tail responsible for the binding of signaling molecules. The cytoplasmic tail of PD-1 contains 2 tyrosine-based signaling motifs, and an immunoreceptor tyrosine-based switch motif. Following T cell stimulation, PD-1 recruits the tyrosine phosphatases SHP-1 and SHP-2 to the immunoreceptor tyrosine-based switch motif within its cytoplasmic tail, leading to the dephosphorylation of effector molecules, such as CD3 zeta (CD3 ζ), protein kinase C-theta (PKC θ) and zeta-chain-associated protein kinase (ZAP)70, which are involved in the CD3 T cell signaling cascade (Riley, 2009; Chemnitz et al, 2004; Sheppard et al, 2004; Okazaki, et al, 2001). The mechanism by which PD-1 down-modulates T cell responses is similar to, but distinct from that of CTLA-4 because both molecules regulate an overlapping set of signaling proteins (Francisco et al, 2010; Parry et al, 2005). As a consequence, the PD-1/PD-L1 pathway is an attractive target for therapeutic intervention in cancer.

2.3 Benefit/Risk Assessment

As of 17 June 2019, 49 patients have received AMG 330 in the ongoing first in human study. Based on the mode of action targeting CD33 which is expressed on myeloid cells, myelosuppression and particularly neutropenia is expected. In addition, infections may be observed based on the myelosuppressive effect. Neutropenia and infections are conditions that are not unexpected in the setting of AML given the nature of this bone marrow disease.

Cytokine release syndrome (CRS) is an identified risk for AMG 330 and respective signs and symptoms were observed in 67% of subjects treated in the study so far.

Checkpoint inhibition may potentially increase the risk for increased frequency and severity of CRS. This risk is mitigated by the requirement for the administration of dexamethasone prior to each step dose of AMG 330. In addition, in cycle 1 of cohort 1, pembrolizumab is introduced 7 days following the step dose of AMG 330 which may reduce the likelihood or severity of CRS. Lastly, treatment with both dexamethasone and tocilizumab will be available for the treatment of clinically significant CRS.

Pembrolizumab has an acceptable clinical safety profile, is indicated for the treatment of patients across a number of malignancies and is in clinical development as an IV immunotherapy for additional advanced tumors. In patients with a history of allogeneic hematopoietic stem cell transplantation (HSCT), acute Graft versus Host Disease (GVHD), including fatal GVHD, has been reported after treatment with pembrolizumab. Based on the benefit of pembrolizumab treatment vs the risk of GVHD assessment, subjects undergone allogenic HSCT within 5 years prior to the study will be excluded.

One of the most frequent adverse events observed during the phase 1a AMG 330 dose escalation study is CRS associated with a release of several potent cytokines including pro-inflammatory IL-6 (Amgen, data on file). Up-regulation of PD-1 expression is a natural pathway employed by immune system to control the inflammation ([de la Fuente, 2012](#)), and there is a risk that blocking PD-1 may potentially interfere with the endogenous protective mechanisms and further aggravate the inflammatory cascade leading to higher grades of CRS in subjects treated with the combination regimen. Thus, PD-1/PD-L1 axis may play a dual role: protect from inflammation and to enable the resistance mechanisms. To mitigate this risk associated with inflammation, the following strategy will be used: administration of dexamethasone prior to each step dose of AMG 330, small step doses to reduce T cell challenge and 7-day duration of each step dose to allow prompt mitigation of potential inflammatory reactions. The potential benefit is to disable the resistance mechanisms to allow improved efficacy.

There is limited potential for other overlapping toxicities because more adverse events associated with pembrolizumab occur later during the treatment whereas AMG 330 related toxicities are acute and observed shortly after dose increase.

The above benefit risk assessment supports the conduct of this clinical study. See the AMG 330 Investigator's Brochure for further data on AMG 330 and Prescribing Information and the pembrolizumab Investigator's Brochure for further data on pembrolizumab.

3. Objectives and Endpoints

Objectives	Endpoints
Primary	

 Evaluate the safety and tolerability of AMG 330 administered in combination with pembrolizumab in subjects with relapsed or refractory acute myeloid leukemia (R/R AML) 	
 Dose-limiting toxicities (DLTs) Treatment-emergent adverse events (TEAEs), treatment-related adverse events (TRAEs), and changes in vital signs, electrocardiograms (ECGs), and clinical laboratory tests
Secondary	

 Evaluate the anti-leukemia activity of AMG 330 administered in combination with pembrolizumab in R/R AML patients 	
 Responses to treatment with AMG 330 administered in combination with pembrolizumab. Response is defined as any of the following: complete remission without minimum residual disease (CR_{MRD}), complete remission (CR), CR with incomplete recovery (CRI), or morphological leukemia-free state (MLFS), or partial remission (all according to the 2017 European LeukemiaNet (ELN) criteria (Döhner et al, 2017)). Duration of response

 Evaluate the pharmacokinetics (PK) of AMG 330 when AMG 330 and pembrolizumab are administered in combination 	
 Descriptive statistics of AMG 330 concentrations and PK parameters.

 Evaluate the immunogenicity of AMG 330 when administered in combination with pembrolizumab 	
 Incidence of anti-AMG 330 antibody formation

Exploratory	

 Evaluate the pharmacokinetics (PK) of pembrolizumab when AMG 330 and pembrolizumab are administered in combination 	
 Descriptive statistics of pembrolizumab concentrations.

 Evaluate the immunogenicity of pembrolizumab when AMG 330 and pembrolizumab are administered in combination 	
 Incidence of anti-pembrolizumab antibody formation

Approved

• Evaluate the relationship between AMG 330 and pembrolizumab exposure and response to treatment	
• Correlate the serum levels AMG 330 and pembrolizumab with changes in tumor burden (exposure/efficacy) and with adverse event incidence (exposure/safety)
--	--

4. Study Design

4.1 Overall Design

This is a phase 1b study assessing safety, tolerability, PK, pharmacodynamics, and efficacy of AMG 330 administered as clV infusion in combination with pembrolizumab in adult subjects with R/R AML.

The study is a non-randomized study and will consist of 2 sequential dosing cohorts. Both cohorts will include AMG 330 and pembrolizumab with the difference being the initiation date for pembrolizumab treatment.

This study will use a staggered enrollment approach. Subject enrollment will start with cohort 1 ([Section 4.1.1](#)). The first subject dosed in cohort 1 will serve as the sentinel subject. Subsequent subjects dosed in cohort 1 will start AMG 330 (█ µg/day) administration once sentinel subject has cleared the study day 21 dose (AMG 330 monotherapy at █ µg/day). Per sponsor determination, if the sentinel subject does not experience a dose-limiting toxicity (DLT) on days 15 to 21 after pembrolizumab is administered, the other subjects in cohort 1 will be allowed to continue the planned treatment schedule. If the sentinel subject experiences a DLT during days 15 to 21, the dose level review team (DLRT) will discuss the case and the decision will be made by the sponsor based on clinical assessments of the adverse event and potential decisions by the sponsor may include stopping AMG 330 and/or pembrolizumab, dose de-escalation of AMG 330, or continuing therapy at full dose. Investigators and sponsor will meet after all subjects in cohort 1 have completed study day 28 (ie, AMG 330 █ µg/day dose level in combination with pembrolizumab) to assess the safety profile. If pre-specified safety criteria are met (≤ 3 out of 10 treated subjects in cohort 1 experienced DLT by day 28), subjects enrolled in cohort 2 ([Section 4.1.2](#)) may proceed with the treatment schedule. Similar to cohort 1, the first subject dosed in cohort 2 will serve as the sentinel subject. Per sponsor determination, if the sentinel subject does not

experience a DLT during the first 7 days, the other subjects in cohort 2 will be allowed to continue the planned treatment schedule.

Safety data will be continuously monitored throughout the whole treatment period. Sponsor in consultation with investigators may reconvene to make appropriate safety measures and adjustments as needed.

Subjects in both cohort 1 and cohort 2 may continue with cycle 2 and beyond of AMG 330 and pembrolizumab up to 6 months if the combination regimen remains tolerable and is deriving clinical benefit in the opinion of the investigator. In both cohorts 1 and 2, subjects continuing with cycle 2 and beyond may be permitted to shorten the duration of AMG 330 step dose levels to 2 to 5 days based on individual clinical experience from cycle 1 and based on the clinical judgement of the investigator and in consultation and agreement with the sponsor. The duration of the combination treatment period for individual subjects may be extended up to 1 year if the subject is deriving clinical benefit in the opinion of the investigator and in consultation with the sponsor. If AMG 330 is discontinued, pembrolizumab may be continued as a monotherapy until disease progression for a maximum of 35 cycles (approximately 2 years). If pembrolizumab is discontinued, AMG 330 may be continued as a monotherapy.

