6.2 Dose Modification

6.2.1 Dose-cohort Study Escalation/De-escalation and Stopping Rules, Dose-Limiting Toxicities (DLTs)

Step Dose Level Determination

A decision to proceed with the next step dose of AMG 330 for each subject in cohorts 1 and 2 will be based on investigator's assessment of safety and upon approval by Sponsor.

In cohort 1, a sentinel subject will be treated first. The minimal interval between treatment start for the sentinel subject and other subjects in the cohort is 21 days. If the sentinel subject has not experienced a DLT by day 14 at █ µg/day AMG 330, he/she will proceed with 200 mg pembrolizumab on day 15 and remain at an AMG 330 dose level of █ µg/day for 7 days (until day 21). If the sentinel subject experiences a DLT during the first 7 days of treatment with AMG 330 at █ µg/day, this subject will be replaced, but the DLT will still be counted towards the study stopping rules. If the sentinel subject does not experience a DLT before or on day 21, the next subjects in the cohort may initiate dosing. If a sentinel subject experiences a DLT, the sponsor will issue a decision based on the evaluation of clinical significance of the adverse event by the DLRT and potential decisions by the sponsor may include stopping AMG 330 and/or pembrolizumab, dose de-escalation of AMG 330, or continuing therapy at full dose.

Cohort 2 will be initiated only after all subjects in cohort 1 completed study day 28 (ie, AMG 330 █ µg/day dose level in combination with pembrolizumab for 7 days), and if the rate of DLT is ≤ 3 out of 10 subjects. After receiving the DLRT recommendation, sponsor will render a final decision and will issue a written notification of the decision to investigators. Further information on dose level review meetings (DLRMs) is provided in [Section 11.3](#).

Individual Stopping Rules

Dosing for an individual will be stopped for any occurrence of a DLT. The event will be reviewed by the investigator and Sponsor for evidence of relationship to treatment and

clinical or medical significance to decide whether dosing may be resumed for the individual and any modifications to the dosing, if appropriate.

Dose Limiting Toxicities

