Please also refer to specific guidance on restart after CRS in [Section 6.8](#). Restarting the infusion after a treatment interruption requires care. The re-start should be performed in the hospital, under supervision of the investigator or designee, if the reason for the interruption was other than a technical issue or the interruption exceeded 4 hours independent of reason. Assessments should be performed after infusion re-start depending on the length of the interruption. The subject should be hospitalized for at least 48 hours after re-start of the infusion.

In case of an AMG 330 infusion interruption of > 24 hours, regardless of the reason for interruption, re-start of the infusion (repeat cycle) should be performed using step doses, which will be defined upon consultation with the sponsor. Only 2 repeat cycles may be performed in cycle 1. For cycle 2 and beyond, additional repeat cycles can be permitted upon discussion and agreement between the investigator and sponsor.

Step doses will be performed within 1 – 2 weeks (\pm 1 day) to return to the interrupted AMG 330 dose level, and the number and duration of repeat step doses will depend on the level of interrupted AMG 330 dose. During this 1-2 weeks, [Table 1-7 Schedule of Activities](#) should be followed (eg, for AMG 330 doses interrupted at [REDACTED] μ g/day and below, 2 step doses can be used: [REDACTED] μ g/day for 3 days followed by [REDACTED] μ g/day for 4 days; for doses interrupted above [REDACTED] μ g/day, 3 step doses can be used: [REDACTED] μ g/day for 1 day followed by [REDACTED] μ g/day for 3 days followed by [REDACTED] μ g/day for 3 days). In case of AMG 330 infusion interruption for < 24 hours, regardless of the reason for interruption, restart of infusion should be performed at the same dose level as the last dose level. Administration of pembrolizumab will remain on the Q3W schedule.

After 2 unsuccessful restarts, the subject may remain on the study and continue AMG 330 treatment with a previously tested target dose that has been well tolerated. The dose of pembrolizumab will remain unchanged.

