9.4.1 Planned Analyses

9.4.1.1 Interim Analysis and Early Stopping Guidelines

Safety data will be reviewed on an ongoing basis. A DLRM will occur when at least 10 treated subjects in cohort 1 have been dosed through study day 28 to determine if the safety profile of initial steps in cohort 1 is acceptable to begin enrollment of cohort 2 or if the study should be stopped. If 3 or more of the 10 treated subjects in cohort 1 experience a DLT by day 28, the guidance to the DLRT is to recommend not to initiate cohort 2. The stopping rule is based on having at least a posterior probability of > 70% that the DLT rate is > 20% assuming a prior distribution of Beta (0.40, 1.60). If the true DLT rate is 10%, 20%, 30%, 40%, or 50%, then the probability of stopping the study at the interim analysis is 7%, 32%, 62%, 83%, 95%, respectively.

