11.3 Appendix 3. Study Governance Considerations

Dose Level Review Meetings

In this study, a dose level review meeting (DLRM) will be conducted 1 time to review and interpret safety data for the purposes of making recommendations about opening cohort 2 and evaluating safety signals for purposes of applying dose cohort/individual stopping rules. The Dose Level Review Team (DLRT) will meet to confirm the decision rules when the following criterion is met:

- at least 10 treated subjects in cohort 1 have been dosed through the end of [REDACTED] µg/day Step Dose (study day 28).

The required DLRT members are the Early Development Lead, Medical Monitor, Global Safety Officer (GSO), and Site Investigators. The DLRT will also include the Early Development Medical Director (Merck) in an advisory role. The DLRT will include Site Investigators from activated sites. The Early Development Lead, Medical Monitor, GSO, and Site Investigators are the only voting DLRT members. The following non-voting Amgen representatives may also be part of the DLRT: clinical study manager, biostatistician, pharmacokinetics (PK) scientist.

The Early Development Lead and Medical Monitor must be in attendance and cannot be represented by a voting designee or delegate. Voting designees can be identified as appropriate by the GSO or Site Investigator(s). A Site Investigator may identify a delegate (eg, sub-Investigator) who is listed in the Delegation of Authority. If a Site Investigator does this, the Site Investigator must provide written agreement with the designee or delegate's vote.

For a DLRM to occur, the Early Development Lead and Medical Monitor must attend, and the GSO or delegate must attend. In addition, a quorum of Site Investigators must be present. A quorum is defined as more than 50% of the participating investigators or their qualified designee. The DLRM will be rescheduled if these requirements are not met.

All available study data, including demographics, investigational product administration, medical history, concomitant medications, adverse events, electrocardiogram (ECG), vital signs, and laboratory results will be reviewed. Data to be reviewed will be unqueried.

DLRM voting will occur as follows: there will be a total of 4 votes, 1 for Early Development Lead, 1 for the Medical Monitor, 1 for the GSO or delegate, and 1 for all of

Approved

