### Study Day:

Study Day is defined as:

Pre study day 1: study day = (date – date of study day 1)

Post study day 1: study day = (date - date of study day 1) + 1

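### The cohort 1 gate counts DLTs by calendar day 28, which need not mean that the intended combination step was completed once a subject has been interrupted and re-stepped

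*Protocol*

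**What the plan says.** **Timing of the gate.** Protocol 4.1 sets the safety review as follows: "Investigators and sponsor will meet after all subjects in cohort 1 have completed study day 28 (ie, AMG 330" at a stated dose level). It thereby explains study day 28 as an AMG 330 dose level in combination with pembrolizumab. Section 6.2.1 agrees ("Cohort 2 will be initiated only after all subjects in cohort 1 completed study day 28") and adds that this means 7 days at that level in combination. Appendix 3 (11.3) convenes the review when "at least 10 treated subjects in cohort 1 have been dosed through the end of" the named step dose, with study day 28 in brackets. Table 4-1 places that step on days 22-28, after pembrolizumab on day 15.

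**Counting.** Section 9.4.1.1 and SAP 7.1 advise against opening cohort 2 "If 3 or more of the 10 treated subjects in cohort 1 experience a DLT by day 28". Sections 4.1 and SAP 3.1 allow it with "≤ 3 out of 10 treated subjects in cohort 1 experienced DLT by day 28".

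**Study day.** SAP 5.3 defines it by the calendar: "study day = (date - date of study day 1) + 1". Protocol 8.1.2 schedules doses and visits from day 1. Nothing resets the count.

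**Interruptions.** Under 6.2.2.1, treatment may resume after up to 21 days. If the gap exceeds 24 hours, "re-start of the infusion (repeat cycle) should be performed using step doses" over 1-2 weeks, at most twice in cycle 1. The same section says that the interrupted cycle is then not evaluable for DLT unless the interrupting event was itself a DLT. Section 4.2.1 permits, but does not require, replacement of non-evaluable subjects.

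**The concern.** For a subject dosed without a break, calendar day 28 and the end of the day 22-28 step coincide. After a non-DLT interruption of more than 24 hours before the step ends, they do not: on day 28 the subject may be off drug or on a lower step.

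Such interruptions are foreseeable. Grade 3 cytokine release syndrome (CRS) requires interruption under 6.2.2.1, but under 6.2.1 it is a DLT only if it has not improved to grade 2 or lower within 5 days. CRS was reported in 63.3% of monotherapy subjects (Protocol 4.3), and section 2.3 allows that PD-1 blockade may aggravate it.

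Taken literally, the rule can then go wrong in two ways. A subject who has not had the gated exposure counts as one of 10 treated subjects without a DLT. Or, if the subject enters the 10 only on finishing the step, a DLT at that step after day 28 is not by day 28. At stake is the single planned review that decides whether to open a cohort receiving both drugs from day 1.

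**Working it through.** **Inputs from the documents.** The rule of 3 or more DLTs in 10, the prior Beta(0.40, 1.60), the criterion of "at least a posterior probability of > 70% that the DLT rate is > 20"% and the stopping probabilities 7/32/62/83/95% at true rates 10/20/30/40/50% (Protocol 9.4.1.1, SAP 7.1). Interruptions of up to 21 days and re-stepping over 7-14 days (Protocol 6.2.2.1).

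**Assumptions, because the documents give no figures.** k is the number of the 10 delayed past day 28 by a non-DLT interruption. s is the share of a subject's DLT risk that falls in the day 22-28 step.

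**Step 1: reproduce the plan's figures.** The posterior after x DLTs in 10 is Beta(0.40 + x, 1.60 + 10 - x). P(rate > 20%) is 0.44 at x = 2 and 0.72 at x = 3, so 3 is the first count above 0.70. For X ~ Bin(10, p), P(X ≥ 3) is 7.0, 32.2, 61.7, 83.3 and 94.5% at p = 10 to 50%. The stated figures reproduce, on the premise that all 10 subjects carry the full risk p. With stopping at 4 or more, the probabilities would be 1, 12, 35, 62 and 83%.

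**Step 2: how late the step can end.** After one interruption, the end day is roughly 28 + length of interruption + re-stepping. Shortest: 28 + 1 + 7 = day 36. Longest: 28 + 21 + 14 = day 63.

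**Step 3: effect on stopping, read literally.** A delayed subject contributes risk p(1 - s) by day 28. The DLT count is the sum of Bin(10 - k, p) and Bin(k, p(1 - s)).

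Example with p = 0.30, s = 1/2, k = 1. The delayed subject's risk is 0.15, and the other nine give P(≥ 3) = 0.5372 and P(= 2) = 0.2668. The result is 0.5372 + 0.15 × 0.2668 = 0.577.

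| Probability of stopping (%) | k = 0 | 1 | 2 | 3 | 4 |
|---|---|---|---|---|---|
| p = 30%, s = 1/2 | 61.7 | 57.7 | 53.5 | 49.1 | 44.5 |
| p = 30%, s = 1/3 | 61.7 | 59.1 | 56.3 | 53.4 | 50.5 |
| p = 40%, s = 1/2 | 83.3 | 80.0 | 76.3 | 72.1 | 67.4 |

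**Step 4: interruption during the step itself.** Protocol 2.3 says AMG 330 toxicity appears soon after a dose increase, so such a subject has already carried much of the step's risk. If half the risk lies in the step and only a quarter of that is lost, the effective s is 1/8. Two delayed subjects at p = 30% then give 59.7%.

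**The case against.** The strongest reply is that the plan already ties day 28 to exposure. Sections 4.1 and 6.2.1 and Appendix 3 all explain it as completing the step, and 4.2, 9.2 and 9.4.1.1 speak of subjects dosed through day 28. On that view a subject on a lower step is not yet one of the 10, and a DLT at the delayed step counts. Section 6.2.2.1 makes the interrupted cycle non-evaluable, and 4.2.1 allows replacement. A subject interrupted for a DLT counts as a DLT, and gaps under 24 hours restart at the same dose. The rule is guidance, the review team sees dosing and adverse event data, and opening cohort 2 needs a unanimous vote.

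Much of this stands. It rules out a stronger reading that a reader might infer: that the gate is diluted however it is read, and so stops less often than stated. If the exposure meaning is applied to both numerator and denominator, nothing is lost.

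The reply does not close the gap in the rule as written. The count is by day 28 among treated rather than DLT-evaluable subjects, and it does not refer to the evaluability sentence in 6.2.2.1. Appendix 3 still puts study day 28 beside the step. Replacement is optional, and under 4.2.1 it may end once 10 subjects are dosed through day 28, the same ambiguous marker. The DLT criterion for receiving less than 70% of planned dose runs over the whole first cycle (77 days in cohort 1), too late to settle a day-28 count.

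**Conclusion.** The point holds as a mismatch between a calendar-based count and an exposure-based intention. It matters only for subjects with a non-DLT interruption of more than 24 hours before the gated step ends. The stated 7/32/62/83/95% apply when no subject is delayed, or when both parts of the count follow completion of the step.

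Under the literal reading at a 30% rate, one delayed subject costs 4.0 points (61.7 - 57.7) with half the risk in the step, or 2.6 points (61.7 - 59.1) with one third. Four cost 17.2 points (61.7 - 44.5) or 11.2 points (61.7 - 50.5). These figures illustrate the effect and are not estimates: both k and s are assumed, and the loss is smaller if the interruption falls within the step. Access to dosing data and the unanimous vote temper the consequence. The correction is still worth making, because voters applying a pre-specified count need to know whom and what to count.

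A larger inconsistency sits at the same gate. Exactly 3 of 10 permits cohort 2 under Protocol 4.1, 6.2.1 and SAP 3.1, but triggers advice against it under Protocol 9.4.1.1 and SAP 7.1. The stated probabilities reproduce only with 3 or more.

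**What to change.** Reconcile Protocol 4.1 (and the matching synopsis text), 4.2, 4.2.1, 6.2.1, 6.2.2.1, 9.2, 9.4.1.1 and Appendix 3, and SAP 3.1, 3.2 and 7.1, so that one exposure-based marker defines both numerator and denominator:

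- A subject is one of the 10 once a DLT has occurred, or once the planned day 22-28 step has been completed with pembrolizumab given.
- Every DLT up to that point counts, whatever the calendar day.
- A subject who meets neither condition is not one of the 10 and may be replaced under 4.2.1.

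This agrees with the non-evaluability sentence in 6.2.2.1 and restores the premise behind the stated probabilities. It is a counting definition and changes no dose or restart rule. Reconcile the thresholds of at most 3 and 3 or more in the same edit, and keep the operating characteristics matched to the threshold retained.

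The cost is wording in two documents and, if subjects are interrupted, a review meeting that may fall some weeks later.

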**Date:** 25 August 2020 **Page 9 of 35** 

This study will use a staggered enrollment approach. Subject enrollment will start with cohort 1 (Section 3.1.1). The first subject dosed in cohort 1 will serve as the sentinel subject. Subsequent subjects dosed in cohort 1 will start AMG 330 ( μg/day) administration once sentinel subject has cleared the study day 21 dose (AMG 330 monotherapy at \(\begin{align\*}
\text{ug/day}\). Per sponsor determination, if the sentinel subject does not experience a dose-limiting toxicity (DLT) on days 15 to 21 after pembrolizumab is administered, the other subjects in cohort 1 will be allowed to continue the planned treatment schedule. If the sentinel subject experiences a DLT during days 15 to 21, the dose level review team (DLRT) will discuss the case and the decision will be made by the sponsor based on clinical assessments of the adverse event and potential decisions by the sponsor may include stopping AMG 330 and/or pembrolizumab, dose de-escalation of AMG 330, or continuing therapy at full dose. Investigators and sponsor will meet after all subjects in cohort 1 have completed study day 28 (ie, AMG 330 µg/day dose level in combination with pembrolizumab) to assess the safety profile. If pre-specified safety criteria are met (≤ 3 out of 10 treated subjects in cohort 1 experienced DLT by day 28), subjects enrolled in cohort 2 (Section 3.1.2) may proceed with the treatment schedule. Similar to cohort 1, the first subject dosed in cohort 2 will serve as the sentinel subject. Per sponsor determination, if the sentinel subject does not experience a DLT during the first 7 days, the other subjects in cohort 2 will be allowed to continue the planned treatment schedule.

Safety data will be continuously monitored throughout the whole treatment period. Sponsor in consultation with investigators may reconvene to make appropriate safety measures and adjustments as needed.

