## 3.3 Adaptive Design

Early stopping for safety rule is specified in Section 7.1.

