### 10. Changes From Protocol-specified Analyses

There are no changes to the protocol-specified analyses.

Protocol Number: 20170646

**Date:** 25 August 2020 Page 25 of 35

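### At exactly 3 DLTs in 10, protocol 4.1, protocol 6.2.1 and SAP 3.1 treat the cohort 2 criterion as met, while protocol 9.4.1.1 and SAP 7.1 advise against cohort 2; only the latter fits the plan's own rule and probabilities

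*Protocol*

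**What the plan says.** Three places set the limit so that three DLTs pass:

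- Protocol 4.1: "If pre-specified safety criteria are met (≤ 3 out of 10 treated subjects in cohort 1 experienced DLT by day 28", after which cohort 2 subjects may go on with treatment.
- Protocol 6.2.1, the section on stopping rules: cohort 2 is initiated only after all of cohort 1 has completed day 28, and "if the rate of DLT is ≤ 3 out of 10 subjects".
- SAP 3.1: "≤ 3 out of 10 treated subjects in cohort 1 experienced DLT by day 28".

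Two places set it so that three DLTs fail:

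- Protocol 9.4.1.1: "If 3 or more of the 10 treated subjects in cohort 1 experience a DLT by day 28", the DLRT is guided to recommend against starting cohort 2.
- SAP 7.1 repeats this rule.

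Protocol 9.4.1.1 and SAP 7.1 also give the basis of the rule: a posterior probability above 70% that the DLT rate exceeds 20%, under a Beta(0.40, 1.60) prior. They state stopping probabilities of 7%, 32%, 62%, 83% and 95% at true DLT rates of 10%, 20%, 30%, 40% and 50%.

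On where the rule lives, SAP 3.3 says: "Early stopping for safety rule is specified in Section 7.1". The protocol has no equivalent pointer, and its synopsis gives no number for this criterion.

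**The concern.** The two sets of text disagree at one result, three DLTs among ten. There a reader of protocol 4.1 or 6.2.1 finds the criterion satisfied, while a reader of protocol 9.4.1.1 finds guidance against going on. The DLRT would meet with both in force.

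The decision matters because cohort 2 is the more exposed cohort. It receives pembrolizumab and AMG 330 together on day 1. Protocol 2.3 presents the delayed start of pembrolizumab in cohort 1 as one way of reducing cytokine release syndrome, and warns that PD-1 blockade may raise its grade.

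If the limit of three were applied, the stopping probabilities printed in protocol 9.4.1.1 and SAP 7.1 would no longer describe the rule in use.

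**Working it through.** **Inputs.** n = 10, prior Beta(0.40, 1.60), posterior threshold 70%, DLT rate threshold 20%, true rates 10% to 50% and stated stopping probabilities 7/32/62/83/95%, all from protocol 9.4.1.1 and SAP 7.1. Candidate boundaries: stop at 3 or more (9.4.1.1, 7.1), or stop at 4 or more (the complement of letting three proceed in 4.1, 6.2.1 and SAP 3.1).

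**Step 1: reproduce the stated probabilities.** With X ~ Binomial(10, p), P(X ≥ 3) = 1 − Σ C(10, x) pˣ (1 − p)¹⁰⁻ˣ over x = 0, 1, 2. At p = 0.30 this is 1 − (0.0282 + 0.1211 + 0.2335) = 0.6172, against the stated 62%. All five true rates:

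| True DLT rate | 10% | 20% | 30% | 40% | 50% |
|---|---|---|---|---|---|
| Stated in the plan | 7% | 32% | 62% | 83% | 95% |
| P(X ≥ 3) | 7.0% | 32.2% | 61.7% | 83.3% | 94.5% |
| P(X ≥ 4) | 1.3% | 12.1% | 35.0% | 61.8% | 82.8% |

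Stopping at three or more matches all five stated figures (0.9453 at the 50% rate rounds to 95%). Stopping at four or more matches none.

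**Step 2: apply the posterior rule.** After x DLTs in 10 the posterior is Beta(0.40 + x, 1.60 + 10 − x). Its upper tail beyond 0.20 is:

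- x = 2, Beta(2.4, 9.6): 0.442
- x = 3, Beta(3.4, 8.6): 0.719
- x = 4, Beta(4.4, 7.6): 0.895

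The 70% threshold is first exceeded at x = 3. The posterior rule and the operating characteristics therefore agree that three DLTs is a result against cohort 2.

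**Step 3: size of the disagreement.** The two limits differ only when X = 3. At p = 0.30, P(X = 3) = 120 × 0.3³ × 0.7⁷ = 0.2668. Then P(X ≤ 2) = 0.3828 and P(X ≤ 3) = 0.3828 + 0.2668 = 0.6496.

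| True DLT rate | 10% | 20% | 30% | 40% | 50% |
|---|---|---|---|---|---|
| P(X = 3), texts conflict | 5.7% | 20.1% | 26.7% | 21.5% | 11.7% |
| Count criterion met, limit 3 | 98.7% | 87.9% | 65.0% | 38.2% | 17.2% |
| Count criterion met, limit 2 | 93.0% | 67.8% | 38.3% | 16.7% | 5.5% |

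**The case against.** The strongest reply is that the count does not open cohort 2 by itself. Protocol 4.1 is permissive. Protocol 6.2.1 makes the count a necessary condition, followed by a DLRT recommendation and a final sponsor decision. Protocol 9.4.1.1 is guidance to that team, and protocol 11.3 requires a unanimous vote to move to cohort 2. This stands as a limit on the consequence. A reader might infer from Step 3 that cohort 2 would open with probability 65% rather than 38% at a true rate of 30%. The documents do not support that, because the figures are chances of meeting the count only. But the reply does not remove the conflict: a team asked to judge against a pre-specified criterion needs one criterion, and at three in ten it has two.

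The second reply is that SAP 3.3 names Section 7.1 as the home of the stopping rule, and SAP 3.1 is only an overview. This has force within the SAP. It does not reach protocol 4.1 or 6.2.1, and SAP 3.1 still prints the other limit. The statement in SAP 10 that "There are no changes to the protocol-specified analyses" does not say which of the protocol's two limits applies.

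A reader might also infer that the plan is deficient because it does not require cohort 1 starts to be held once a third DLT occurs before the planned meeting. The documents do not support raising that to a defect. Safety is reviewed continuously, dosing stops and is reviewed for each individual DLT, each AMG 330 step needs sponsor approval, and the sponsor may reconvene with investigators, so a pause is already possible. No accrual rate is given from which to show what a mandatory hold would save.

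**Conclusion.** The point holds as an internal inconsistency in a decision threshold. The limit in protocol 4.1, protocol 6.2.1 and SAP 3.1 is wrong as written. Neither the Bayesian rule nor the stated probabilities need correction: both are reproducible and both correspond to stopping at three or more.

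The conflict arises with probability 20% to 27% if the true day-28 DLT rate is between 20% and 40% (20.1%, 26.7% and 21.5% at the three rates calculated). At 30%, the wrong limit raises the chance of meeting the count criterion by 26.7 percentage points.

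These figures assume exactly ten subjects with independent outcomes and a common DLT probability. The meeting is triggered by at least ten subjects. With eleven, three DLTs give a posterior of 0.664, below the threshold, but both limits are written for ten and the conflict is at that number.

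**What to change.** Change the limit from three out of ten to two out of ten in protocol 4.1, protocol 6.2.1 and SAP 3.1. Leave protocol 9.4.1.1 and SAP 7.1 as they are.

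The cost is one number in three places. Sample size, prior, threshold and stated operating characteristics are unchanged, because the edit restores the rule those figures were calculated for.
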